1. PURPOSE OF THE STUDY

a. Brief Summary

This proposed pilot study will directly compare two delivery methods for a body acceptance/ eating disorder program to assess whether this program is more effective when delivered virtually. We will evaluate whether virtual groups produce greater reductions in eating disorder risk factor symptoms (pursuit of the body ideal, body dissatisfaction, dieting, dietary restraint and negative affect), eating disorder symptoms, and future onset of eating disorders when all other factors are held constant.

b. Objectives

Aim 1: Evaluate whether virtual delivery of an eating disorder prevention program produce greater reductions in eating disorder risk factor symptoms, eating disorder symptoms, and eating disorders when compared to in-person groups. Results will provide critical information regarding the possibility of broad implementation via virtual delivery. Aim 2: Determine any distinguishing factors that make virtual delivery more effective than in-person delivery in producing a larger reduction in outcomes. Results will highlight any differences between the two forms of delivery that can be transferred to in-person groups, improving both conditions.

c. Rationale for Research in Humans

This study must use humans due to the nature of body image disturbances and eating disorders occurring only in humans, but not in other animals to our knowledge. Because the programs require speech as a method of communication, human subjects are necessary due to the fact animals do not engage in this form of communication.

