2. STUDY PROCEDURES

a. Procedures

1) Young adult females will learn about the study through the study team's recruitment efforts, including online advertisements through Facebook, Instagram, Craigslist, and

Reddit, flyers posted near college campuses flyers posted in high traffic areas on Stanford's campus (dorms, dining halls) and distributed/promoted by Vaden Student Health Services, listservs for different communities/clubs, social media platforms (Instagram, Facebook, Twitter), Reddit

2) Potential participants who express interest will be given a link to a secure online Qualtrics screening questionnaire for the research study (this link will also be available directly from advertising material). Upon completion of the questionnaire, potential participants will then be contacted via phone or email. After eligibility is determined, they will be scheduled for a consent and baseline assessment.

3) After it has been determined that potential participants are a good fit for the study and they have offered consent to participate, they will be instructed to complete a short survey-based assessment.

Assessments

- a) EDDI: A standardized measure that measures the presence of an eating disorder and the severity of the characteristic psychopathology of eating disorders.
- b) Survey: Demographics, Thin Ideal Internalization Scale, Body Dissatisfaction Scale, Positive and Negative Affect Scale and Dutch Restrained Eating Scale

4) All participants will receive the same 4 session eating disorder prevention program, albeit virtual groups or in-person groups. Participants will be randomized to a virtual delivery condition condition or an in-person delivery condition. Participants have a 50/50 chance of being randomized to either condition. Participants will be assigned to a 5–6-person group run by trained peer educators, and engage in 4 sessions of the Body Project over the course of 4 weeks. These sessions will take place either online using Zoom, a videoconferencing tool, or in-person on Stanford's campus (following university COVID-19 safety protocols and precautions).

5) Once the 4 sessions have been completed, participants will be contacted to complete a short set of post-test surveys.

Assessments

- a) EDDI: A standardized measure that measures the presence of an eating disorder and the severity of the characteristic psychopathology of eating disorders.

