This pilot study is comparing the effects of a virtual delivery versus in-person delivery of an eating disorder prevention program. Everyone in the trial will receive the Body Project, an effective eating disorder prevention program, meaning that everyone who participates will benefit. There will be no alternative courses of treatment to offer. This program is designed for prevention, to prevent the likelihood of onset of an eating disorder. Thus, it is not intended to treat any conditions. The only other alternative would be to not participant in this study. There are no known risks associated with participation in this eating disorder prevention program, although some sensitive topics may cause participant's discomfort. This program has the potential to aid participants in resolving some or all struggles and difficulties with body image. Additionally, this study will not hinder participants with a DSM-5 eating disorder from continuing or pursuing any outside treatment whilst they are enrolled in the study. Previous research has shown that there are stronger reductions in eating disorder symptoms for participants with a DSM-5 eating disorder than participants without an eating disorder.

f. Will it be possible to continue the more (most) appropriate therapy for the participant(s) after the conclusion of the study?

If there are participants who meet criteria for a DSM-5 eating disorder at the termination of the study, the appropriate referrals will be provided. This study will not interfere with their current levels of care or their future levels of care.

g. Study Endpoint(s)

If there is such a discrepancy between the two different conditions, they will be evaluated by the principal investigators in terms of terminating the study prematurely. Otherwise, we shall examine the program's effectiveness at the end of the study and study participation will be completed within 24-weeks, including a 3-month follow up after the conclusion of Body Project groups.

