8. PARTICIPANT POPULATION

- a. Planned Enrollment
 - (i) We expect to enroll 60 participants at Stanford.
 - (ii) We expect to enroll 60 participants total at all sites. Stanford is the only site of this study.
 - (iii) Healthy, adult females 18-40 are the target population for this eating disorder prevention program. Using participants that fit this description enables the research team to evaluate the effectiveness of virtual delivery versus in-person delivery of this prevention program and discern the specific factors that may contribute to virtual delivery being more effective in reducing eating disorder risk factors and symptoms and risk for future eating disorders.

- b. Age, Gender, and Ethnic Background

Target participants will be females age 18-40, we will not exclude on the basis of ethnic background.

- c. Vulnerable Populations

Young adult females are included in this study because they are at elevated risk for future eating disorder onset. Information on the risks and benefits of the program and their rights and welfare will be addressed in the Informed Consent forms.

If participants are too young (below 18), they will be excluded from this study. We plan to ask for dates of birth from all interested participants during the screener in order to determine if they are at an appropriate age to participate in the study. Dates of birth from all interested participants will be required during the screener in order to determine if they are at an appropriate age to participate in the study.

- d. Rationale for Exclusion of Certain Populations

The purpose of this study is to evaluate two delivery methods for a body acceptance/eating disorder prevention class to test whether the program is more effective when implemented virtually. Children are not the target population of this study, as we are examining the effectiveness of the program in adult women, which are typically above 18 years of age.

- e. Stanford Populations

Stanford students, employees, or laboratory personnel may be eligible to participate in the research study. We cannot estimate how many that might be. If any such participants are enrolled, they will follow standard procedure as any participant would and complete a consent form.

- f. Healthy Volunteers

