Additionally, all families who call the Stanford clinic for services are asked about their willingness to be contacted for research. Individuals who may potentially meet study inclusion criteria will be called and asked if they are willing to hear about a Stanford research study.

h. Eligibility Criteria

i. Inclusion Criteria

- i. Female
- ii. Ages 18 - 40

iii. Fluently speak and read English and have access to a computer or tablet with internet
iv. Must live within the United States

ii. Exclusion Criteria

N/A

i. Screening Procedures

Interested participants will be asked to fill out a brief online screening questionnaire. Only information pertaining to the inclusionary & exclusionary criteria will be included in the questionnaire. Participants have the option to terminate the online screening questionnaire at any time. The participant will be contacted to schedule an assessment upon review of their questionnaire. For participants that complete the online screener, the participants rights will be clearly stated before proceeding with the screening. Additionally, they can call the research personnel prior to continuing if they have any questions.

j. Participation in Multiple Protocols

As a part of the informed consent process, subjects will be asked if they are participating in any other research projects. Their participation in other protocols will not exclude them from participation in this study.

k. Payments to Participants

N/A

l. Costs to Participants

N/A

m. Planned Duration of the Study

The estimated duration of the entire study is eight months, in line with the timeline for completion of a Master's thesis and summer quarter conferral.

- i. The screening will consist of the online questionnaire (about 10 minutes), and the baseline assessment (about 1-2 hours).
- ii. Active participation will be 4 months (4 weeks of Body Project sessions, and 3 month follow-up assessment)
- iii. Analysis of participant data will take about 2-3 months.

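### Does the undefined outcome of future eating-disorder onset, in a trial that may enrol women who already have a disorder, call for a change to the analysis plan?

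*Protocol*

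**What the plan says.** Protocol 1a lists the outcomes on which the two delivery modes will be compared and ends with "eating disorder symptoms, and future onset of eating disorders when all other factors are held constant". Aim 1 (1b) speaks more loosely of reductions in eating disorders. Section 8a(iii) refers to factors that may make virtual delivery "more effective in reducing eating disorder risk factors and symptoms and risk for future eating disorders".

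Nothing in the entry criteria (8h) concerns diagnosis. The inclusion items are sex, age, English with device access, and US residence, and the exclusion criteria are marked not applicable. On screening, 8i states: "Only information pertaining to the inclusionary & exclusionary criteria will be included in the questionnaire". Section 2e expects some enrolled women to have a disorder: "this study will not hinder participants with a DSM-5 eating disorder from continuing or pursuing any outside treatment whilst they are enrolled". Section 2f adds: "If there are participants who meet criteria for a DSM-5 eating disorder at the termination of the study, the appropriate referrals will be provided".

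The EDDI, described as measuring both presence and severity of an eating disorder, is scheduled at baseline, posttest and 3 months. Diagnostic interviews are added at 3 months (2a, items 3, 5 and 6).

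The SAP gives one model, a linear mixed model of posttest score on condition and pretest score with a random intercept for cohort. It has no model for a diagnosis and no analysis of the 3-month visit.

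**The concern.** Onset can occur only in a woman who does not already have the disorder. If baseline cases are enrolled and no at-risk set is defined, a count of diagnoses at follow-up mixes new cases with persisting ones. A difference between arms in remission could then be read as a difference in prevention, which is the central claim of a prevention programme. Followed literally, the SAP also yields no onset comparison, although the Protocol names one and schedules diagnostic interviews. At stake would be either a promised result that never appears or one with the wrong denominator.

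**Working it through.** There is no figure in the plan to reproduce. The documents give no prevalence, onset rate, remission rate or sample-size calculation.

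**Inputs from the documents:** 60 women, allocated 1:1 (about 30 per arm); posttest missingness 12-24% (SAP).

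**Assumptions:** baseline prevalence p = 10-30%; 3-month onset i = 2-10%; remission r = 25-75%; the SAP's missingness carried over to follow-up diagnosis.

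**1. Women at risk and expected onsets**
- At risk = 60 × (1 − p): 54 at p = 10%, 42 at p = 30%, or 27 to 21 per arm.
- Onsets: 42 × 0.02 = 0.84 to 54 × 0.10 = 5.4 in total.
- With missingness: 42 × 0.76 × 0.02 = 0.64 to 54 × 0.88 × 0.10 = 4.75.

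**2. Precision of a correctly defined comparison** (Newcombe 95% interval for the risk difference; p = 20% gives 24 at risk per arm)

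| Onsets per arm | Half-width, percentage points |
|---|---|
| 0/24 vs 0/24 | 13.8 |
| 1/24 vs 1/24 | 16.4 |
| 2/24 vs 2/24 | 18.5 |
| 2/21 vs 2/21 (12% missing) | 20.6 |
| 2/18 vs 2/18 (24% missing) | 23.1 |

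The 1/24 row is closest to a 5% onset rate (1/24 = 4.2%).

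**3. Power, two-sided 5% level (assumed), 16 to 30 at risk per arm**
- Assumed onset of 5% vs 2.5%, 10% vs 5%, or 20% vs 10%. The last pair reaches beyond the range above and favours detection.
- Fisher's exact test: below 10% in every case. Normal approximation: 6-19%.
- 80% power would need 906, 435 and 199 per arm respectively.

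**4. What the wrong denominator could do**
- Share of follow-up diagnoses that are persisting cases = p(1 − r) / [p(1 − r) + (1 − p)i].
- At p = 0.20, r = 0.50, i = 0.05: 0.10 / (0.10 + 0.04) = 71%. Over the full ranges it runs from 22% to 94%.
- If the SAP's linear model were fitted to a yes/no diagnosis in all women, the condition coefficient would be about p × (difference in persistence) + (1 − p) × (difference in onset).
- With equal onset and remission 20 points higher in one arm, this is −0.20p: −2, −4 and −6 points at p = 10, 20 and 30%.
- Simulation (30 per arm, onset 5% in both arms, remission 40% vs 60%, cohort term omitted because the SAP reports an intraclass correlation near zero, 6,000 runs) gives means of −1.8, −3.8 and −5.9 points, with standard deviations of 6.6, 7.8 and 8.5. The shift is below one standard error throughout.

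**5. Is that analysis planned?** The SAP does say its model is fitted for each measure, and the EDDI is a measure. But the outcome in the equation is a posttest score, and the one eating-disorder outcome the SAP names is a count of symptoms. Neither document calls for a 0/1 model in all women, so step 4 describes a hypothetical analysis.

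**The case for a change.** The strongest reply is that a low event count does not excuse leaving a named outcome undefined. When events are few, the choice of denominator dominates whatever is reported. Putting it right needs no new data, only a definition and a small table. Aim 1's looser wording also leaves room for a reader to take remission for prevention.

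The textual part stands: onset is named in 1a, is not defined, and has no analysis. If onset is reported at all, new cases belong over women without a disorder at baseline, with baseline cases shown separately.

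The rest is weaker. The SAP already reports observed intraclass correlations and missingness, so a definition written now would be post hoc and could not restore pre-specification. The text in 8a(iii) concerns risk, which the risk-factor scores also address, and the Study Endpoint(s) section (2g) does not list onset. That leaves the Brief Summary of a pilot as the one clear statement of onset as a compared outcome.

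Two neighbouring points do not add to the case. The Protocol calls its target population healthy (8a and 8f) yet foresees enrolled women with a disorder (2e); those passages should be reconciled as drafting. How the EDDI is given at baseline is unclear, since 2a says "they will be instructed to complete a short survey-based assessment" while 8m allows longer for "the baseline assessment (about 1-2 hours". A difference in mode between visits is possible but not established.

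**Conclusion.** No change to the plan follows. This is missing detail that a competent analyst fills in the usual way, and the score comparisons, which are what the SAP sets out, remain sound without it. The most that defining onset could add is a descriptive, post hoc count of roughly 1 to 5 events, with an interval of about ±14 to ±23 percentage points on the risk difference in the cases worked. No conclusion about delivery mode could rest on it. Those sizes depend on assumed prevalence and onset, but the judgement is not sensitive to them: even at 20% vs 10% onset with 30 at risk per arm, Fisher's test has under 10% power. The judgement would change if a comparative claim about onset or prevention were made from diagnoses counted in all women, and neither document plans that.

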2. STUDY PROCEDURES

a. Procedures

1) Young adult females will learn about the study through the study team's recruitment efforts, including online advertisements through Facebook, Instagram, Craigslist, and

Reddit, flyers posted near college campuses flyers posted in high traffic areas on Stanford's campus (dorms, dining halls) and distributed/promoted by Vaden Student Health Services, listservs for different communities/clubs, social media platforms (Instagram, Facebook, Twitter), Reddit

2) Potential participants who express interest will be given a link to a secure online Qualtrics screening questionnaire for the research study (this link will also be available directly from advertising material). Upon completion of the questionnaire, potential participants will then be contacted via phone or email. After eligibility is determined, they will be scheduled for a consent and baseline assessment.

3) After it has been determined that potential participants are a good fit for the study and they have offered consent to participate, they will be instructed to complete a short survey-based assessment.

Assessments

- a) EDDI: A standardized measure that measures the presence of an eating disorder and the severity of the characteristic psychopathology of eating disorders.
- b) Survey: Demographics, Thin Ideal Internalization Scale, Body Dissatisfaction Scale, Positive and Negative Affect Scale and Dutch Restrained Eating Scale

4) All participants will receive the same 4 session eating disorder prevention program, albeit virtual groups or in-person groups. Participants will be randomized to a virtual delivery condition condition or an in-person delivery condition. Participants have a 50/50 chance of being randomized to either condition. Participants will be assigned to a 5–6-person group run by trained peer educators, and engage in 4 sessions of the Body Project over the course of 4 weeks. These sessions will take place either online using Zoom, a videoconferencing tool, or in-person on Stanford's campus (following university COVID-19 safety protocols and precautions).

5) Once the 4 sessions have been completed, participants will be contacted to complete a short set of post-test surveys.

Assessments

- a) EDDI: A standardized measure that measures the presence of an eating disorder and the severity of the characteristic psychopathology of eating disorders.
- b) Survey: Demographics, Thin Ideal Internalization Scale, Body Dissatisfaction Scale, Positive and Negative Affect Scale and Dutch Restrained Eating Scale

6) At 3-months, participants will be contacted to complete a short set of post-test surveys at follow-up and diagnostic interviews will be given.

Assessments

- a) EDDI: A standardized measure that measures the presence of an eating disorder and the severity of the characteristic psychopathology of eating disorders.
- b) Survey: Demographics, Thin Ideal Internalization Scale, Body Dissatisfaction Scale, Positive and Negative Affect Scale and Dutch Restrained Eating Scale

b. Procedure Risks

The research procedures described above poses non-significant risks for participants and the research staff involved in this project are fully trained in their assigned responsibilities. Adherence to the program protocol will be monitored by the PIs for this pilot study and participants will be instructed that they may drop out of the study at any point.

c. Use of Deception in the Study

No deception will be used.

d. Use of Audio and Video Recordings

Video recordings of the virtual sessions will occur using the built-in recording tool on Zoom and an audio recorder for the in-person sessions. The recordings are necessary to ensure adherence to protocol and quality of both the virtual and in-person delivery of the Body Project. No PHI (participant health information) or participant identifying information will be recorded. In the event that this does occur, this information will be edited out before it is saved to the hard drive and shared with any other study personnel. All video files will be downloaded and stored in the HIPPA compliant Stanford Medicine Box hard drive.

e. Alternative Procedures or Courses of Treatment

This pilot study is comparing the effects of a virtual delivery versus in-person delivery of an eating disorder prevention program. Everyone in the trial will receive the Body Project, an effective eating disorder prevention program, meaning that everyone who participates will benefit. There will be no alternative courses of treatment to offer. This program is designed for prevention, to prevent the likelihood of onset of an eating disorder. Thus, it is not intended to treat any conditions. The only other alternative would be to not participant in this study. There are no known risks associated with participation in this eating disorder prevention program, although some sensitive topics may cause participant's discomfort. This program has the potential to aid participants in resolving some or all struggles and difficulties with body image. Additionally, this study will not hinder participants with a DSM-5 eating disorder from continuing or pursuing any outside treatment whilst they are enrolled in the study. Previous research has shown that there are stronger reductions in eating disorder symptoms for participants with a DSM-5 eating disorder than participants without an eating disorder.

f. Will it be possible to continue the more (most) appropriate therapy for the participant(s) after the conclusion of the study?

If there are participants who meet criteria for a DSM-5 eating disorder at the termination of the study, the appropriate referrals will be provided. This study will not interfere with their current levels of care or their future levels of care.

g. Study Endpoint(s)

If there is such a discrepancy between the two different conditions, they will be evaluated by the principal investigators in terms of terminating the study prematurely. Otherwise, we shall examine the program's effectiveness at the end of the study and study participation will be completed within 24-weeks, including a 3-month follow up after the conclusion of Body Project groups.

3. BACKGROUND

a. Past Experimental and/or Clinical Findings

The severity of eating disorders are extreme, with all eating disorders having an increased risk of mortality and increased likelihood of functional impairment and suicide attempts than other psychiatric disorders (Smink, van Hoeken and Hoek, 2012; Arcelus et al., 2011). The economic burden of eating disorders is massive and only increasing. An estimated 28.8 million Americans will have an eating disorder in their lifetime and the economic burden of treating an eating disorder is \$64.7 million each year (Sonneville & Lipson, 2018). For the current cost of treating one eating disorder, between 32 and 186 cases could be prevented (Akers, Rohde, Shaw and Stice, 2021). This does not even take into consideration the fact that 80% of individuals with eating disorders never seek treatment and current treatments fail to produce lasting results, with less than 40% of eating disorder patients making a full recovery (Swanson et al., 2011). Thus, there is a critical need for a paradigm shift in our approach to eating disorders: transitioning from reactive medicine to preventive medicine as a public mental health issue.

The Body Project eclipses numerous other reputable eating disorder prevention programs that have been evaluated. Indeed, solely the Body Project has proved effective in a) reducing eating disorder risk factors, symptoms, and onset through 2-4 year follow-up b) reduce these outcomes when compared to several other valid alternative interventions c) proven to affect the intervention target (appraisal of the thin ideal) d) affect objective biological outcomes (reduction in brain reward circuitry response to thin models) and e) produce effects that are consistently replicated independent of one another (Stice et al., 2017). Furthermore, the robust economic value of the Body Project makes it an ideal candidate for furthering the field of eating disorder prevention, with delivery costs of the Body Project being significantly less than the current costs for treating an eating disorder (\$20,300 for CBT for BN to approximately \$119,200 for treatment of AN) (Akers, Rohde, Shaw and Stice, 2021).

In a piloted virtual trial of the Body Project conducted last year, virtual groups showed significantly greater pretest-to-posttest reductions in pursuit of the thin ideal, body dissatisfaction, dieting, negative affect, and eating disorder symptoms when compared to in- person groups. In fact, the Body Project groups conducted last year produced the largest reductions in outcomes that have ever been observed when it was delivered virtually via zoom. Thus, virtual delivery could make broad implementation possible and result in better outcomes, which could be effectively carried over to in-person groups as well.

b. Findings from Past Animal Experiments

N/A

